**Print Name** 

# 3 Abbreviations and Definitions

# Table 1 Abbreviations and Explanations

Term	Definition
ACT	Active Clearance Technology
AFib	Atrial Fibrillation
CABG	Coronary Artery Bypass Graft
CFR	US code of Federal Regulations
CRF	Case Report Form
CRO	Contract Research Organization
CVA	Cerebrovascular Accident
IEC	Independent Ethics Committee
FDA	Food and Drug Administration
GCP	Good Clincial Practice
HIPAA	Health Insurance Portability and Accountability Act
ICF	Informed Consent Form
ICU	Intensive Care Unit
IFU	Instructions for Use
NIS	US National Inpatient Sample
IRB	Institutional Review Board
ITT	Intent to Treat
MDR	Mandatory Medical Device Reporting (US)
MI	Myocardial Infarction
PCI	Percutaneous Coronary Intervention
PF-CA	PleuraFlow Clearance Apparatus
PF-CT	PleuraFlow Chest Tube
PMCF	Post Market Clinical Follow-up Study
PHI	Personal Health Information
POAF	Postoperative Atrial Fibrillation
PP	Per Protocol
RBS	Retained Blood Syndrome
SAE	Serious Adverse Event
UADE	Unanticipated Adverse Device Effect
VAD	Ventricular Assist Device
VTE	Venous Thromboembolism
WBC	White Blood Count
WMA	World Medical Association

# 4 Background and Rationale

Post Operative Atrial Fibrillation (POAF) is one of the most common complications after heart surgery, occurring in 20% to 60% of patients, and is a leading cause of hospital costs and readmissions.[1] Based on findings from our institutional clinical database at the Montreal Heart Institute, the local incidence after cardiac surgery is approximately 25%. In the NIH POAF study, the Montreal Heart Institute result's show an incidence of 35% of POAF (33/95 recruted patient). POAF is associated with an increased risk of mortality and morbidity, predisposes patients to a higher risk of stroke, requires additional treatment, and increases the costs of the post-operative care.[2] There are currently no reliable preventative approaches that can be uniformly applied to all patients in a prophalactic fashion to reduce this complication. Various drug regimins have been tested, but must be selectively applied and can have undesirable side effects.[3] The development of a universally applicable prophalactic approach that reduces POAF broadly would be a great advance for cardiac surgery patients.

Chest tube clogging has long been a concern in early post operative recovery.[11] Methods such as chest tube stripping or milking, or opening chest tubes to remove clots with balloon catheters have been utilized but have been shown to be ineffective and possibly even harmful, leading to a significant unmet need on how to best maintain chest tube patency after surgery.[12-14] Preventing chest tube occlusion to facilitate

maximal drainage of blood around the heart in the early hours of recovery after cardiac surgery has the potential to alleviate this problem. The PleuraFlow® System with Active Clearance Technology® (ClearFlow Inc. Anaheim, CA), was developed by surgeons to facilitate postoperative blood evacuation by preventing chest tube occlusion.[11] This system, which is placed in the operating room at the end of the procedure, is utilized in the ICU to prevent chest tube occlusion in the first 24 hours or until the patients stops bleeding during early recovery. PleuraFlow was shown in pre-clinical studies to be highly effective in preventing RBS.[15, 16] After initial regulatory approval, Montreal Heart Institute was the site of the world's first human use of this technology. All the surveyed surgeons noted that the device was not any more difficult to insert than a conventional chest tube and was easy to assemble and use. A majority of surveyed nurses felt that the device was more time efficient than stripping, milking, or tapping the chest tubes to keep them open and felt it represented an easy to implement solution to the common problem of chest tube clogging.[17] In a subsequent study, it has been reported that the use of PleuraFlow in a universal use protocol significantly reduces RBS and POAF. Study results showed a statistically significant 42% reduction in re-interventions for RBS complications among a 256 patient cohort where the PleuraFlow® system was used prospectively in comparison to a 1,849 historical cohort. Additionally, there was a statistically significant 30% decrease in POAF documented in the treatment group versus the historical control.[18]

Given the findings that this device has already been shown to be readily implemented into our work flow in the ICU in a preliminary published study, and the new findings of reduced POAF and RBS, the purpose of this study is further evaluate these findings in a randomized controlled setting. Therefore, we hypothesize that active clearance of chest tubes to optimize evacuation of shed mediastinal blood in the immediate postoperative period will reduce the incidence of re-interventions for POAF and RBS and lower overall morbidities after cardiac surgery. Should this prove to be a valid hypothesis, protocols to keep chest tubes patent in the early hours after cardiac surgery can be developed and implemented.

# 5 Device

The PleuraFlow® system is a commercial product regulatory cleared in the United States (US) (K093565) and by Health Canada. It will be used according to indications for use and the current Instructions for Use (IFU).

The PleuraFlow® Active Clearance Technology® System consists of a PleuraFlow® chest tube (PF-CT) and PleuraFlow® Clearance Apparatus (PF-CA). Together these two pieces make up the PleuraFlow® System. The device incorporates an integrated internal tube Clearance Apparatus designed to maintain patency of the chest tube, thus enhancing fluid evacuation from the thoracic cavity. The active mechanism consists of an external to internal magnetic coupling that controls the movement of a metal wire inside the Movement of the internal wire to clear the chest tube is actuated chest tube. externally, without breaking the internal sterile field (see Figure 1). The PleuraFlow® ACT® has been tested in an experimental animal model at the Cleveland Clinic. In a head to head comparison with a same sized conventional 32 Fr chest tube in the setting of heavy bleeding, the PleuraFlow® drained significantly more, and significantly prevented residual hemothorax. When the 20 Fr minimally invasive system was tested against a 32 Fr conventional tube, again there was significantly superior drainage and significantly less retained blood and clot with the PleuraFlow® System. This was the first time a small diameter drainage tube was found to be superior to a larger diameter tube. During initial clinical use physicians and nurses rated the PleuraFlow® system positively for its ability to be incorporated into the postoperative workflow of managing the drainage of patients after heart surgery.

[figure not shown]

Figure 1: The PleuraFlow® ACT® System Overview

# 6 Indications for Use and Contraindications:

#### 6.1 Indications

The PleuraFlow® ACT® System is indicated for use as an adjunctive device during open surgical procedures in order to prevent fluid accumulation within the operative site after closure of the surgical wound. The device is indicated for use in thoracic surgical procedures.

#### 6.2 Contraindications

The PleuraFlow  $^{\ensuremath{\$}}$  System is contraindicated for patients with a history of intolerance to implantable silicone materials.

# 7 Good Clinical Practice

This clinical investigation will be conducted in compliance with regulatory requirements intended to:

- Protect the rights, safety and well-being of human subjects;
- Ensure the scientific conduct of the clinical investigation and the credibility of the clinical investigation results;
- Define the responsibilities of the manufacturer and principal investigator, and;

Assist sponsors, investigators, ethics committees, regulatory authorities and other bodies involved on the conformity assessment of medical devices.

# 8 Study Design

This is a prospective, randomized, two-arm, single blinded, single-center Post Market Clinical Follow-Up (PMFC) study. An interim analysis allowing for an early look at efficacy is planned after 300 randomized subjects have completed their 30-day follow-up. This interim analysis is proposed following the results of a retrospective study done at the Montreal Heart Institute on more than 300 patients, comparing AF rate between patients with pleuraflow and control patients. After a propensity score adjustment, a difference of 16% was obtained (AF rate of 9% in the pleuraflow group vs 25% in the control group). Since this might be a sign that the difference between the two arms is larger than expected, an interim analysis is planned after 300 patients.

## 8.1 Test Arm

The test arm consists of consecutively enrolled cardiac surgery patients receiving  $\leq$  two (2) PleuraFlow® chest tubes with Active Clearance Technology® and  $\leq$  two (2) other commercially available standard chest tubes.

## 8.2 Control Arm

The control arms consist of consecutively enrolled cardiac surgery patients receiving  $\leq$  four (4) commercially available standard chest tubes.

## 8.3 Control and Test Arms

In all arms, one (1) chest tube must be placed in the anterior mediastinum. The other chest tube(s) may be placed at the discretion of the operator. Chest tubes with internal diameter 28 FR to 32 FR shall be used for the single anterior mediastinal chest tube.

The Montreal Heart Institute is required to participate in a pre-study roll-in phase prior to participating in this clinical study. The purposes of the pre-study roll-in phase are to:

- Allow the users at participating sites to familiarize themselves with the product use and with ACT;
- Implement Clinical Use Protocols provided by ClearFlow, Inc. to all commercial users as part of product training, and;
- Demonstrate consistency and compliance with the clinical use protocols.

Pre-study roll-in phase requirements are:

- Consecutive use of  $\mathsf{PleuraFlow}^{\$}$  system on patients having cardiac surgeries during a 1 month period.

# 9 Study Population

### 9.1 Demographics

-Up to 508 evaluable post-cardiac surgery female and male subjects, 18 years of age and older will be consecutively enrolled in the study.

- Subjects are required to meet all inclusion criteria and none of the exclusion criteria to be included in this PMCF study. Subjects must be informed about this study and a written and signed informed consent must be obtained from the subject prior to cardiac surgery.

## 9.2 Inclusion Criteria

Subjects will be required to meet all Inclusion Criteria:

- 9.2.1Admission for CABG, valve replacement or valve repair surgery, or a combination of these surgeries. Surgery must be done through a mediansternotomy;
- 9.2.2Procedure on ascending aorta and/or aortic arch that do not require deep hypothermic arrest (defined as  $\leq$  14° C);
- 9.2.3Must be in sinus rhythm (SR) for previous 30 days prior to the index surgery and at the start of the index surgery. No patient with history of atrial fibrillation;
- 9.2.4Sign the Institutional Review Board (IRB) or Independent Ethics Committee (IEC) approved Informed Consent Form after the nature of the study has been explained and questions/concerns have been addressed.

#### 9.3 Exclusion Criteria

Subjects will be required to meet none of the Exclusion Criteria:

- 9.3.1 Admitted for surgical treatment of arrhythmia;
- 9.3.2 Admitted for cardiac surgery requiring implantation/explantation of a Ventricular Assist Device (VAD) or heart transplant;
- 9.3.3 Cardiac surgical procedure that requires deep hypothermic arrest (as defined above);
- 9.3.4 Admitted for Transcatheter aortic valve replacement (TAVR);
- 9.3.5 New or active endocarditis or myocarditis that is not adequately controlled with medication and/or requires surgical intervention;
- 9.3.6 Documented inherited bleeding disorders;
- 9.3.7 History or known allergies to the device materials; or
- 9.3.8 Participation in another clinical investigation. If a subject has recently completed participation in another drug or device clinical investigation, the subject must have completed that study at least thirty (30) days prior to being enrolled in this clinical study.

# **10** Procedural Steps and Methods

This study is on label and, accordingly, there are no specific procedures to follow. The test article (PleuraFlow® System) will be used at the end of the cardiac surgery per standard of care. The Sponsor is blinded to the study results. Data will be revealed to the Sponsor after the last enrolled subject has exited the study (end of postoperative day 30 or hospital discharge, whichever occurs last).

### 10.1 Informed Consent and Subject Enrollment

Investigators shall obtain a signed informed consent from each subject before enrolling as a study subject. Each subject shall sign and date the IRB/IEC approved Informed Consent Form (ICF). A subject who is unable to read and/or provide signature can participate in this clinical study, provided that a legal representative with signature authority signs and dates the ICF on behalf of the subject.

Subjects shall be given sufficient time to review the ICF and ask questions before signing. The investigator or designee shall be available to answer any questions about this clinical study. An independent witness shall be present during the consenting process, and will sign and date the ICF.

The device and procedures that are part of this PMFC study are performed after a scheduled cardiac surgery and are part of routine standard of care. There are no procedures or treatments that are required for the purposes of the study. The research part of the study is the data collection of subjects' history, peri- and post-cardiac surgery and postoperative clinical appointment.

# **10.2** Screening and Enrollment

Participating sites shall screen consecutive patients who are admitted for cardiac surgery. Patients who could meet the study eligibility criteria will be offered to participate in this clinical study. Screen failures and reason(s) for screen failure shall be documented on study-specific logs and provided to the Sponsor periodically.

Patients who meet the clinical study eligibility criteria and sign the ICF shall be enrolled and randomized prospectively **before** surgery to either receive the test article (PleuraFlow® System) and other commercial chest tubes (test arm), or to receive commercial chest tubes only (control arm), as part of their cardiac surgery (day 0). Any commercial chest tube is eligible for use in this clinical study. Enrollment period is from consent through 30 days post index surgery.

#### 10.3 Training

#### Product Training

Prior to initiation of the trial, a ClearFlow, Inc. representative will train the surgeons and the supporting staff in the operating room and in the intensive care unit (ICU) using a training curriculum.

The device shall be used according to the commercial IFU (Manual of Operations). ClearFlow, Inc. has created Clinical Use Protocols (Manual of Operations) for the use of PleuraFlow® ACT®. The Clinical Use Protocols are in accordance with the IFU. Users will follow the specific procedural steps outlined in the attached commercial Clinical Use Protocols (Manual of Operations).

Placement (locations) and number of PleuraFlow® System(s) and commercial chest tubes are dictated by this PMCF study protocol (See section 6).

#### **10.4 Documentation**

Training will be documented. The trainee must sign and date the training record. Training must be completed and training records must be signed and dated before the staff is allowed to perform specific clinical investigation related tasks delegated to them by the PI.

#### **10.5 Randomization**

Subjects who meet eligibility criteria will be randomly assigned in a 1:1 fashion to either the Test arm or the Control arm.

The point of randomization is before the start of the index surgery. Subject assignment will be provided to the operating surgeon at that time.

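### The surgeon is told the arm before surgery, although the device is placed only at the end and sinus rhythm at the start of surgery is not yet confirmed: randomise and disclose later

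*Combined protocol and SAP*

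**What the plan says.** **Timing of randomisation and disclosure.** Section 10.2: "Patients who meet the clinical study eligibility criteria and sign the ICF shall be enrolled and randomized prospectively", with the next words placing this before surgery. Section 10.5: "The point of randomization is before the start of the index surgery", followed by "Subject assignment will be provided to the operating surgeon at that time".

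**Timing of the device.** Section 10 says the system "will be used at the end of the cardiac surgery per standard of care". Section 4 also has it placed in the operating room when the procedure ends.

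**Eligibility.** Criterion 9.2.3 requires sinus rhythm for the preceding 30 days and again when the index surgery starts. The primary analysis is by intention to treat (section 2.15).

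**Tubes.** The test arm gets up to two PleuraFlow tubes and up to "two (2) other commercially available standard chest tubes" (section 8.1). The control arm gets up to "four (4) commercially available standard chest tubes" (section 8.2). Both arms must have one anterior mediastinal tube; beyond that, "The other chest tube(s) may be placed at the discretion of the operator" (section 8.3). Section 10.3 (Product Training) instead says that the placement and number of PleuraFlow systems and "commercial chest tubes are dictated by this PMCF study protocol (See section 6"). Section 6 covers only indications and contraindications.

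**The concern.** The surgeon needs the arm when the tubes go in. Under sections 10.2 and 10.5 the surgeon has it for the whole operation, and the supplied text does not say why. Anything done between the start of surgery and tube placement is therefore done with the arm known, in a trial whose primary endpoint, postoperative atrial fibrillation (POAF), may respond to what happens in that operation. Early disclosure buys no benefit that the documents name.

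The same timing creates an eligibility gap. One inclusion criterion refers to a moment after randomisation. A patient who loses sinus rhythm in between no longer meets it but is already in the intention-to-treat comparison. The supplied text does not say how such a patient is handled, and any decision about that patient would be made with the arm known.

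**Working it through.** **1. The plan's own figure.** Inputs from section 2.15: POAF 25% against 15%, significance level 0.0476, power 80%. Sidedness is not stated; two-sided reproduces the figure.

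n = [z(α/2)·√(2p̄q̄) + z(β)·√(p₁q₁ + p₂q₂)]² / (p₁ − p₂)²

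With p̄ = 0.20, z(α/2) = 1.981 and z(β) = 0.842: [1.981·√0.32 + 0.842·√0.315]² / 0.01 = (1.121 + 0.472)² / 0.01 ≈ 254 per arm. The stated size reproduces, and neither the timing issue nor its fix changes it.

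**2. Order of events.**

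| Step | When | Section |
|---|---|---|
| Consent | Before surgery | 9.1, 10.1 |
| Randomisation; arm given to surgeon | Before the start of surgery | 10.2, 10.5 |
| Sinus rhythm required | At the start of surgery | 9.2.3 |
| Operation | After the start | – |
| Device placed | End of surgery | 4, 10 |

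Two intervals follow from this order:

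- *Randomisation to start of surgery.* The rhythm criterion cannot be confirmed until this interval ends, so eligibility is incomplete at randomisation. The documents give no frequency for loss of sinus rhythm here and no length for the interval.
- *Start of surgery to tube placement.* The surgeon operates knowing the arm. The documents give nothing from which to size an effect of this on POAF, so no figure is offered.

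**3. What later disclosure does and does not cover.** It covers both intervals above. It does not cover the number and position of tubes, because the surgeon must know the arm to place them.

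**4. Tube choices: an illustration only, which does not support later disclosure.** Section 4 cites a prospective study in which extra drainage tubes went with a fall in POAF from 23.8% to 11.3%, or 0.238 − 0.113 = 0.125. Assume, without support in the documents, that this difference applies to the choices open here, and that fuller drainage differs between arms by 10% or 20% of patients.

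- Shift in POAF: 0.125 × 0.10 = 1.25 points; 0.125 × 0.20 = 2.5 points.
- No device effect, 254 per arm, pooled test at 0.0476, final look only: the chance of a significant result favouring the device goes from 2.4% to 4.9% (25% against 23.75%) or 9.4% (25% against 22.5%).
- Reverse imbalance with the planned effect: power goes from 80% to 68–70% or 53–57%, the ranges depending on whether the test rate is raised or the control rate lowered.

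A by-arm table of tubes placed (254 per arm, two-sided 0.05) would show a 5-, 10- or 20-point imbalance with probability 20%, 62% or 99.5% if about half of patients get fuller drainage, and 27%, 74% or 99.9% if one arm is at 20%. For 45% against 55%: (0.10 − 1.96 × 0.0444) / 0.0442 = 0.295, giving 62%.

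**The case against.** - **The calculable harm is not the one later disclosure prevents.** This stands. A reader might infer from the figures above that early disclosure raises the false-positive rate to 5–9% and that late disclosure restores it. The documents do not support that. The figures model a tube imbalance that would remain possible under late disclosure, and they rest on assumed imbalances and one cited study.
- **A by-arm table detects but does not correct.** This stands, and it would usually miss a 5-point imbalance. It is a descriptive check.
- **The arms are drainage packages.** Sections 8.1 and 8.2 define them by tube mix, and sections 10 and 10.1 describe on-label, routine use. Tube choices that follow from assignment may then be part of the strategy that intention to treat compares. This stands, and is a further reason not to call such a difference a false positive.
- **Loss of rhythm precedes device use and should balance by randomisation.** This stands as to direction, and the interval may be short. The defect that remains is that eligibility is incomplete at randomisation.
- **Early randomisation looks deliberate.** Section 10.2 emphasises the word before. That shows intent but gives no reason.
- **The Manual of Operations was not supplied.** Its clinical use protocols, and the roll-in on compliance with them (section 8.3), may narrow discretion or explain early disclosure. Its case report forms may already record tubes (section 12). So it cannot be said that tube data are not collected, only that the supplied analysis text and outcome lists plan no report of them by arm.

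**Conclusion.** The point holds as a weakness in design timing. Randomisation and disclosure come before surgery, the device comes at the end, and one inclusion criterion is assessed in between. Operative conduct is exposed to knowledge of the arm without a stated need, and a patient can enter the intention-to-treat comparison before eligibility is settled.

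The size and direction of any bias are unknown. A reader might infer that the trial is biased towards the device; nothing in the documents shows that. The conclusion rests on the supplied text alone, and an explanation in the Manual of Operations could weaken it. It is worth acting on because the change is cheap, not because harm has been demonstrated.

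The conflict over tube placement between section 8.3 and section 10.3 is separate. The pointer to section 6 is probably a numbering slip, since the tube rules are in section 8, but whether position is discretionary or dictated must be reconciled.

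**What to change.** 1. **Main change.** Amend sections 10.2 and 10.5: keep consent before surgery, but randomise and disclose the arm as late as practical before chest-tube placement, after sinus rhythm at the start of surgery is confirmed.
2. **Secondary step, also the fallback if late randomisation is impractical.** Report the number and position of tubes actually placed, by arm, as a descriptive check. Add them to the case report form if they are not already there.
3. **Text.** Reconcile sections 8.3 and 10.3 on placement, and correct the pointer to section 6. No placement rule is proposed.

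**Cost.** One protocol amendment, at most a short form entry, and one table. The real burden is logistic: the assignment must be opened in the operating room, with both tube types at hand, for up to 508 patients at the two hospitals named in the synopsis. No extra patients are needed.
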